volume were generated across both groups and time as in the cross-sectional study. At baseline, the CDR 0 subjects had a mean (SD) hippocampal volume of 2081(354) mm³ on the left side and 2600 (481) mm³ on the right side, while the CDR 0.5 subjects had a mean hippocampal volume of 1717 (224 mm³) on the left side and 2186 (370 mm³) on the right side. At follow-up, the CDR 0 subjects showed a hippocampal volume reduction of 82 mm³ on the left side and 142 mm³ on the right side, while the CDR 0.5 subjects showed a hippocampal volume reduction of 164 mm³ on the left side and 236 mm³ on the right side. ANOVA indicated a significant group effect on the rate of hippocampal volume loss ($F = 7.81$, $df = 1,42$, $p = 0.008$). This difference persisted after covarying hippocampal volumes for total cerebral brain volume ($p = 0.007$), total intra-cranial volume ($p = 0.008$) and scan interval ($p = 0.015$).

[figure not shown]

Figure 2. Comparisons from Baseline to Follow-up (two years) in CDR 0.5 and CDR 0 Elder Subjects. Displacement maps were used to visualize the across-time difference in hippocampal structure in the two subject groups. Cooler colors (blue to purple) signify areas of inward deformation over time. In the CDR 0.5 subjects, areas of inward deformation were more widespread and included more of the lateral edge of the hippocampus, while in the CDR 0 subjects, areas of inward deformation were smaller and confined to the head

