Hippocampal volumes, total cerebral volumes and total intracranial volumes were not significantly correlated with any of the measures of cognitive decline. However, among the first 10 eigenvectors (which explained > 80% of the variance in hippocampal shape), eigenvector 3 coefficients were correlated with two measures of the rate of cognitive decline. More negative eigenvector 3 coefficient values were significantly correlated with increasing sum-of-boxes slope values ($r = -0.34$, $p = 0.03$, two-tailed) and with increasing NPI slope values ($r = -0.31$, $p = 0.05$, two-tailed). A trend correlation was observed between more negative eigenvector 3 coefficient values and decreasing MMSE total scores ($r = 0.29$, $p = 0.07$, two-tailed), but no correlation was observed between eigenvector 3 coefficient values and ADAS-Cog total scores ($r = -0.11$, $p = .50$, two-tailed). These correlations were unchanged after taking into account total cerebral brain volume, total intracranial volume, and age.

[figure not shown]

Figure 3. Pattern of Hippocampal Shape Variation Correlated with the Outcome of Donepezil Treatment.

The two panels illustrate the extremes of hippocampal shape variation in eigenvector 3, that were characteristic of DAT subjects who showed clinical worsening (top panel) and improvement (bottom panel) during donepezil treatment. Cooler colors (blue to purple) signify areas of inward deformation and warmer colors signify areas of outward deformation relative to the mean shape of all subjects.

The pattern of hippocampal shape variation represented by eigenvector 3 is shown in Figure 3. The pattern of shape variation associated with greater cognitive decline during donepezil treatment was similar to the pattern of shape deformation previously shown to discriminate CDR 0.5 and CDR 0 subjects (see Figure 1), and to be associated with disease progression changes CDR 0.5 subjects over time (see Figure 2) (i.e., inward deformation of the lateral prominence of the hippocampus). In turn, the relative absence of this pattern of deformation in hippocampal shape was associated a more favorable outcome during donepezil treatment. These results suggest that hippocampal shape may be a predictor of the capacity of DAT patients to respond to donepezil.

STUDY DESIGN

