The hippocampus, parahippocampal gyrus and cingulate gyrus have been selected as the neuroanatomical variables to be assessed during the proposed funding period based on a review of the literature and our own prior results. Explicit neuroanatomical rules were used to define the boundaries of these brain structures. To generate templates, structural boundaries were outlined using semiautomated routines that combine autotracing and manual tracing techniques available in Analyze™. Analyze™ permits the simultaneous viewing of any point in the scan from three orthogonal planes. Autotracing functions encircle a selected region of uniform density by enclosing all contiguous pixels of similar density. The selection of tissue of a particular density is then achieved by setting thresholds that define the brightness of the pixels in the area of interest. Surrounding tissue of a different density (threshold) is deleted from the picture, leaving only the tissue of interest. When autotracing fails to segment tissues of similar density, the tissue is manually traced.

d. MR Scanning Protocols and Image Preprocessing

MR scans will be collected at the baseline assessment and after two years using a 1.5T VISION system (Siemens Medical Systems) with a UNIX based host computer (Sun Microsystems), actively shielded gradients, and echo-planar capability. Subjects will be positioned on the table with their canthomeatal line perpendicular to the table; head position stability is facilitated with adjustable cushioned head supports. A standardization object is placed in the field of view on the left side of the head for each MR scan. Prior to the scan, the

procedure is explained in detail to each subject, and techniques to tolerate small spaces and avoid claustrophobia are described. The MRI scans do not involve the administration of any contrast agent.

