All MR scans will be acquired using a turbo-FLASH sequence (TR=20, TE=5.4, Flip angle=30° ACQ-1, Matrix=256X256, Scanning time=13.5 minutes), that 3D datasets with 1 mm x 1 mm x 1 mm isotropic resolution across the entire cranium (Venkatesan and Haacke, 1997). A 2D set of proton density and T2 weighted images with standard 5-mm thicknesses will also be acquired for clinical interpretation of any unsuspected disease conditions, and to assess the number of white matter hyperintensities in each subject. [name], Associate Professor of Radiology, oversees MR scan acquisition at Washington University School of Medicine, and together with his team, monitors scanner drift on a daily basis. Frequency, receiver gain, reference transmitter voltage, and signal-to-noise are examined. Phantoms of known dimensions are imaged and the gradient calibration is checked to make certain the correct size is registered. Protocols are also employed to check for ghosting artifacts. Further tests and calibration adjustments are performed when needed. Shims are used when needed to correct for field inhomogeneities.

For image analysis, the raw MR data are transferred to a SGI workstation at Washington University where 3D reconstructions of brains are obtained using Analyze™ software (Rochester, MN). MR data files are identified by number only to maintain blind conditions for image analysis. Because the turbo-FLASH MR sequence yields 1 mm isotropic voxels, rescaling to correct discrepancies due to voxel isotropy is not necessary. Signed 16 bit MR datasets are compressed to unsigned 8 bit MR datasets by linearly rescaling the voxel intensities, such that voxels with intensity levels at two standard deviations above the white matter mean (corpus callosum) are mapped to 255, and voxels with intensity levels at two standard deviations below the CSF mean (third ventricle) are mapped to 0.

As a final step in the preprocessing of MR images, neuroanatomical landmarks are placed by [name]. In each scan, twelve landmarks are placed at the external boundaries of the brain, and at the points where the anterior and posterior commissures intersect the midsagittal plane (Haller, et al, 1997). Additional landmarks are also placed at selected points along the principal axis of the hippocampus (Csernansky, et al, 1998).

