Construction of the surface between gray and white matter then places us in a position to determine the probabilities of CSF, gray matter and white matter voxels within the segmented subvolume as a function of the closest distance from the voxel to this surface (see embedded surface represented by the yellow line in Figure 5, panel C). Specific algorithms to compute these distances were first developed in Miller, et al (2000), for several types of cortical subvolumes, and then refined by Ratnanather, et al (2003), for specific cortical regions. Figure 5, panel D shows an example of a profile that shows the probabilities of encountering CSF, gray matter and white matter voxels as a function of the distance to the gray matter/white matter surface in a single subject.

which a predetermined percentage of voxels are accounted for (e.g., 80%, 90%, etc.) can then be used as an estimate of cortical thickness across the region.

Cortical metrics such as gray matter volume and thickness are then generated from the probability profiles. The gray matter volume is equivalent to the cumulative sum of gray matter data in the profile. In turn, graymatter thickness is based on the distances from the gray matter/white matter surface where pre-assigned percentiles of voxels (e.g., 85%, 90% or 95%) are reached. Finally, gray matter surface area is computed by summing up all the triangles of the triangulated graph of the surface within the selected subvolume.

g. Assessment of Total Intracranial and Cerebral Volumes

Assessment of total intracranial and brain volumes is needed to control for generalized brain volume reduction, as has been reported by some investigators. Mathalon, et al (1993), have examined the issue of correction for head size and brain volume in such circumstances and shown that such corrections decrease unwanted variance while improving the ability to detect meaningful biological variation (e.g. correlations between brain structure volumes and age).

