Variables to assess changes in structural volume, thickness, and shape (for the hippocampus) will be generated as described above. Bivariate correlations between changes in clinical and neuroanatomical variables will be estimated using non-parametric statistics (Spearman's rho). To assess whether observed bivariate relationships are independent of each other, a stepwise multiple regression model will be developed including all independent neuroanatomical variables and slope values for the CDR sum-of-boxes scores as the dependent variable.

To test **hypothesis 2** (*The rate of decreasing hippocampal and cortical volumes, thinning of the cingulate and parahippocampal cortices, and changing hippocampal shape will be equal in DAT subjects that are untreated and in DAT subjects that are treated with donepezil alone, but greater than the rate of volume loss, thinning and hippocampal shape change in DAT subjects that are treated with the combination of donepezil and*

memantine.), rates of change for the various neuroanatomical variables will be compared in DAT subjects that are untreated, that are treated with donepezil alone, that are treated with the combination of donepezil and memantine, and in nondemented comparison subjects. These analyses will be performed using simple difference scores (follow-up minus baseline) for volume and thickness variables. To compare rates of change in hippocampal shape across groups, a MANOVA using eigenvectors derived from the time 1-to-time 2 transformation covariance will be performed (see above). The distributional characteristics of each of these variables will be examined prior to hypothesis testing. Finally, non-parametric (Wilcoxon rank sum tests) statistics will be used to compare the groups.

i. Sample Size and Power Considerations

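### Volume change is tested as a raw mm³ difference with no term for starting volume, intracranial volume or scan interval, although section g says volume correction is needed

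*Combined protocol and SAP*

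**What the plan says.** **STUDY DESIGN, section g.** "Assessment of total intracranial and brain volumes is needed to control for generalized brain volume reduction". The section cites work showing that "such corrections decrease unwanted variance while improving the ability to detect meaningful biological variation", and then describes how both volumes are obtained from each scan.

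**STUDY DESIGN, section h.** For Hypothesis 2: "These analyses will be performed using simple difference scores (follow-up minus baseline) for volume and thickness variables", after which "non-parametric (Wilcoxon rank sum tests) statistics will be used to compare the groups". For Hypothesis 1, changes are related to cognitive slopes by Spearman's rho, followed by a stepwise regression on the neuroanatomical variables. Neither part mentions intracranial volume, total cerebral volume, baseline structure volume or scan interval.

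**PRELIMINARY STUDIES, the two-year longitudinal pilot.** For the same endpoint: "This difference persisted after covarying hippocampal volumes for total cerebral brain volume". The text adds intracranial volume and scan interval as further covariates.

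**PRELIMINARY STUDIES, the donepezil pilot.** "These correlations were unchanged after taking into account total cerebral brain volume, total intracranial volume, and age". This sentence is about baseline shape (eigenvector 3) against cognitive slopes. It shows the group's practice of adjusting, but it is not evidence about volume change.

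**STUDY DESIGN, section a.** The four groups are not randomised. Groups 1 and 4 come from the ADRC archive, Group 2 from the initial funding period and Group 3 from new recruits. A subject who stops early has the second scan at that time rather than at two years.

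**The concern.** The plan measures quantities that it says are needed for correction, and the pilot used them. The analysis section then fixes tests that leave them out, because a rank-sum test on a difference score takes no covariate.

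Subtracting baseline removes a fixed additive level but not a multiplicative one. Two subjects who each lose the same fraction of the hippocampus differ in mm³ lost if one started smaller. Randomisation would balance starting size on average, but these groups come from different sources and periods. A Group 3 that started smaller would look slowed at an identical fractional rate. One that started larger would have part of any slowing hidden.

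Hypothesis 2 is also worded in terms of rates, whereas the planned outcome is not divided by the time between scans.

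**Working it through.** **1. Reproduce the pilot test.** The longitudinal pilot (18 CDR 0.5, 26 CDR 0) reports F = 7.81 on 1 and 42 df, p = 0.008. The F distribution gives p = 0.0078, which agrees. The standardised difference is d = √[7.81 × (1/18 + 1/26)] = 0.86.

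**2. What the pilot covariates did.** Each adjusted p-value is turned back into F, assuming 41 error df after one covariate, and then into d in the same way.

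| Covariate | p reported | F implied | d implied |
|---|---|---|---|
| none | 0.008 | 7.81 (reported) | 0.86 |
| total cerebral volume | 0.007 | 8.06 | 0.87 |
| intracranial volume | 0.008 | 7.77 | 0.85 |
| scan interval | 0.015 | 6.45 | 0.78 |

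Brain and intracranial volume made almost no difference. Scan interval moved the result most. Baseline hippocampal volume was not among the covariates reported.

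**3. Does the scale matter?** Pilot baseline means and losses in mm³:

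| | Left baseline | Left loss | Fraction | Right baseline | Right loss | Fraction |
|---|---|---|---|---|---|---|
| CDR 0.5 | 1717 | 164 | 9.55% | 2186 | 236 | 10.80% |
| CDR 0 | 2081 | 82 | 3.94% | 2600 | 142 | 5.46% |

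- Ratio of losses in mm³: 164/82 = 2.00 left, 236/142 = 1.66 right.
- Ratio of fractional losses: 9.55/3.94 = 2.42 left, 10.80/5.46 = 1.98 right.

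The choice of scale changes the contrast when groups start at different sizes.

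**4. A starting-size gap between DAT groups.** The protocol gives two DAT samples: 1833 and 2242 mm³ (left, right) in the 46-subject cross-sectional replication, and 1717 and 2186 mm³ in the longitudinal pilot.
- Left gap: (1833 − 1717)/1833 = 116/1833 = 6.3%.
- Right gap: (2242 − 2186)/2242 = 56/2242 = 2.5%.
- False difference at equal fractional loss: 116 × 0.0955 = 11 mm³ left and 56 × 0.108 = 6 mm³ right.

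For scale, section i speaks of decreases of 50 mm³ over two years; 11 and 6 mm³ are 22% and 12% of that. A false difference of the full 50 mm³ would need a baseline gap of 50/0.0955 = 524 mm³ left or 50/0.108 = 463 mm³ right.

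**5. Noise from starting size, relevant to Hypothesis 1.** Under proportional loss, starting size contributes an SD of 0.0955 × 224 = 21 mm³ left and 0.108 × 370 = 40 mm³ right. The pilot contrasts of 82 and 94 mm³ average 88, so the implied SD of change is about 88/0.857 = 103 mm³, assuming the reported F applies to the average of the sides. Removing the starting-size part gives √(103² − 21²) = 101 and √(103² − 40²) = 95 mm³, a reduction of about 2% to 8%.

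**6. Scan interval.** Pilot intervals ran from 1.0 to 2.6 years (CDR 0.5) and 1.4 to 4.1 years (CDR 0). At a constant rate, a subject losing 164 mm³ over two years shows 82 mm³ if scanned at one year. A raw difference cannot separate that from slower atrophy.

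**The case against.** **The pilot adjustment changed nothing.** This is the strongest reply, and for intracranial and brain volume it stands. It does not cover starting hippocampal volume, which was not adjusted for. It also comes from a comparison of DAT with controls, not of DAT groups with each other.

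**Proportional loss is not shown.** This is correct. No figure in the documents relates baseline volume to loss within DAT. The larger right hippocampus lost more mm³ in both pilot groups, which fits, but that compares structures rather than subjects. If small hippocampi mark faster disease, a proportional scale could itself mislead. That is a reason to keep raw mm³ as a sensitivity analysis.

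**Section h may not list every covariate.** HUMAN SUBJECTS foresees gender as a covariate that section h also omits, and DATA MANAGEMENT allows transformations. Those transformations are triggered by distributional problems, however, not by size, and the tests actually named take no covariate.

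**Stronger readings that are not supported.** A reader might infer that head size materially biases the comparison; step 2 gives no sign of it. A reader might also infer that scanner scale drift does so, from "Further tests and calibration adjustments are performed when needed" and from the absence of any analytic use for the object in "A standardization object is placed in the field of view on the left side of the head for each MR scan". An assumed linear error of 0.25% to 1% would shift volume by 13 to 52 mm³ left and 16 to 66 mm³ right. But no drift is documented, section d describes daily monitoring and phantom checks, and bias would need the shift to differ between groups. Finally, the documents do not support saying that the raw scale would by itself create or hide a memantine effect: the gap in step 4 yields 11 and 6 mm³.

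**Conclusion.** The concern holds in a limited form. Sections g and h do not agree. Followed as written, section h leaves out the correction that section g calls for, and does not account for starting volume or scan interval in non-randomised groups.

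The starting-size effect is modest: about 11 mm³ left and 6 mm³ right. This assumes loss proportional to starting volume and a gap like that between the two DAT samples in the protocol. Those samples are not the treatment groups, whose baseline volumes are not given. The 50 mm³ used for scale is not clearly a between-group difference in section i.

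The change should be made because it is cheap, uses data already planned, and removes a choice of scale that would otherwise be open to argument after the results are known.

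**What to change.** In section h:

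- **Outcome.** Analyse volume change as annualised proportional change, ln(V2/V1) divided by the scan interval in years. Divide thickness change by the scan interval.
- **Hypothesis 2.** Compare groups in a linear model with baseline intracranial volume as covariate, on ranks if the model assumptions fail.
- **Hypothesis 1.** Use the same change measure with partial Spearman correlations adjusted for intracranial volume.
- **Sensitivity.** Report the raw mm³ differences as now planned.
- **Secondary only.** Report adjustment for change in total cerebral volume separately, because that change occurs after treatment starts and could absorb part of a treatment effect.

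The cost is wording, slightly more analysis, one or two degrees of freedom, and main results that compare less directly with published mm³ figures. No new data are needed.

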Clinical diagnostic criteria for DAT at the ADRC and MDC at Washington University correspond to those established by the NINCDS-ADRDA Work Group (McKhann, et al, 1984), and have a 93% accuracy for the histopathological presence of AD at autopsy ([name], et al, 1996; Berg, et al, 1998). All subjects are assessed annually using clinical, psychometric, and behavioral measures that are valid for the detection of very mild stages of DAT (Berg, et al, 1998). The clinical measures include staging of dementia severity using the CDR ([name], 1993).

Treatment will be administered in this study in an open-label fashion. All DAT subjects selected for this study will already have been selected for donepezil therapy alone or the combination of donepezil and memantine, regardless of their participation in the proposed study. Therefore, randomization to a lesser form of drug therapy or placebo would be below the standard of care and therefore unethical (Kawas, et al, 1999; Knopman, et al, 1998). Also, by selecting subjects for this study who have already been identified as candidates for drug therapy, our sample should be representative of clinical populations prescribed such treatments.

All clinical evaluations will be performed blind to the results of neuroanatomical assessments. Therefore, no systematic bias will be introduced related to our main hypotheses involving correlations between the results of these biological assessments and treatment response. Subjects will be excluded from this study if they have already had a substantial period of treatment (i.e., more than 8 weeks) with a cholinesterase inhibitor. Vitamin E treatment (400-800 U/day), non-steroidal drugs and Cox-2 inhibitor drugs will be permitted during the treatment period, since this situation is typical of clinical settings in which cholinesterase inhibitors and memantine are administered, so long as the doses of these treatments remain constant throughout the treatment period. However, other drug treatments under investigation for their efficacy in DAT will not be permitted during the treatment period.

Prior to initiation of treatment, all subjects will undergo a comprehensive diagnostic evaluation using NINCDS-ADRDA criteria (McKhann, et al, 1984), as well as the CDR ([name], 1993), the Alzheimer Disease Assessment Scale (ADAS; Rosen, et al, 1984), which includes a concise battery of cognitive tests (i.e., the ADAS-Cog), the Mini-Mental State Examination (MMSE; Folstein, et al, 1975), and the Neuropsychiatric Inventory (NPI), to assess the severity of dementia and behavioral symptoms related to dementia. Emergent

side-effects of donepezil and memantine treatment will be recorded using an instrument standard to clinical trials (Treatment Emergent Side-effect Scale [TESS]).

Drug treatment will begin with 5 mg/day of donepezil for six weeks. After six weeks of such treatment, the subjects' symptoms will be re-evaluated and any side-effects of treatment assessed and recorded. If no serious side-effects of donepezil are encountered, the dose of donepezil will be increased to 10 mg/day. For subjects prescribed the combination of donepezil and memantine, memantine (20 mg/day) will be added to the drug treatment regimen after the dose of donepezil has been established (i.e., at six weeks). Again, memantine will be initially started at 10 mg/day and increased to its full dose only if no serious side-effects are encountered. Subsequent evaluations will then be performed every 12 weeks for two years. All evaluations after 6 weeks will include the complete set of clinical and cognitive (i.e., ADAS-Cog) assessments, and a full diagnostic evaluation will be repeated annually (see Flowchart below). MR scans will be collected at baseline and after two years of treatment for all subjects who complete the entire period of treatment. For any subject that discontinues their participation in the study prematurely, the second MR scan will be collected at that time.

Clinical Trial Flowchart

Baseline	Six Weeks	12 Weeks	Every 12 Weeks For Two Years
Donepezil →→ → → → (5 mg/d)	Donepezil → (5 to 10 mg/d)		
	Memantine → (10 to 20 mg/d)		
Diagnosis			Repeat Diagnosis at 1 and 2 Yrs
CDR ADAS-Cog MMSE	CDR ADAS-Cog MMSE	CDR ADAS-Cog MMSE	CDR ADAS-Cog MMSE
NPI	NPI TESS	NPI TESS	NPI TESS
MRI			Repeat MRI at 2 Yrs

Subjects will be selected for this study if they meet NINCDS-ADRDA criteria for DAT at baseline (McKhann, et al, 1984), and have a score of 0.5 or 1 on the CDR ([name], 1993). Subjects who no longer meet diagnostic criteria for DAT after one or two years of treatment, or who are diagnosed with another dementing illness, will still be followed for the remainder of the study, but their data will be evaluated separately from those subjects who continue to meet all inclusion and exclusion criteria. Based upon our prior experience with this population of subjects in the ADRC (Berg, et al, 1992), we expect such changes in diagnosis to be rare. The great majority of DAT subjects rated as 0.5 or 1 using the CDR are proven at autopsy to show the neuropathological signs of AD ([name], et al, 1996; Berg, et al, 1998). Although it is possible that there will be subjects whose symptoms progress to the point where they can no longer be evaluated, this again should be rare given the demonstrated reliability and validity of the CDR across a wide range of severity of dementia symptoms (Berg, et al, 1992; [name], et al, 1993).

Inclusion Criteria: 1) meets NINCDS-ADRDA criteria for DAT, 2) CDR score of 0.5 or 1, 3) 50-80 years of age, 4) able to give informed consent or has a primary caregiver or legal guardian, who can give informed consent.

Exclusion Criteria: 1) other psychiatric (e.g., depression) or neurological (e.g., CVA) disorders that would confound the assessment of dementia symptoms, 2) history of loss of consciousness, and 3) unstable or severe

medical illness (e.g., hepatotoxicity) that would make donepezil or memantine treatment or participation in other aspects of the study unsafe.

b. Selection of Instruments for Clinical Evaluation

Total sum-of-box scores from the CDR ([name], 1993) will be used as the primary outcome measure. In our prior long-term studies (i.e., 4 to 10 years) of DAT subjects with very mild-to-mild DAT (i.e., CDR 0.5 to CDR 1), sum-of-boxes scores have been shown to be highly sensitive to disease progression and to have minimal ceiling or floor effects (Berg, et al, 1988; Berg, et al, 1992). In addition, so that the results of this study can be compared with large clinical treatment trials of DAT subjects, ADAS-Cog scores, total MMSE scores and total NPI scores will be used as secondary outcome measures (see below).

To perform the CDR, a clinician trained in its use rates the subject's cognitive abilities and function in *six* categories: memory, orientation, judgment and problem solving, community affairs, home and hobbies, and personal care. Impairment is rated 0-5 in the direction of increasing severity in each of these categories or *boxes*. The sum of these *box scores* is then compiled to yield CDR scores as follows: CDR 0 (no dementia); CDR 0.5 (very mild dementia); CDR 1 (mild dementia); CDR 2 (moderate dementia); and CDR 3 (severe dementia). Interrater reliability for the CDR is very high (Burke, et al, 1988), and subjects categorized with DAT over time using the CDR, including the CDR 0.5 category, are confirmed at autopsy as having AD with 96% accuracy ([name], et al, 1988; [name], et al, 1991; Berg and [name], 1994). Clinicians at our Center all routinely receive extensive training in the use of the CDR, and interrater reliability is routinely monitored. Finally, sum-of-boxes scores have been shown to be a highly useful an index of dementia severity over time (Berg, et al, 1988; Berg, et al, 1992). In a study of 68 DAT subjects with beginning CDR scores of 0.5 or 1 followed for 4 to 10 years, sum-of-boxes scores declined in a relatively linear fashion and had very few ceiling or floor effects (i.e., all 68 DAT subjects could be rated using this measure at baseline and 24 months later) (Berg, et al, 1992).

As mentioned above, the ADAS-Cog (Rosen, et al, 1984), the MMSE total score (Folstein, et al, 1975), and the NPI will be used as secondary outcome measures. These measures have been previously used in treatment trials of DAT subjects as both primary and secondary measures of symptom severity, and have been demonstrated to be sensitive to the effects of cholinesterase inhibitors (Farlow, et al, 1998; Rogers, et al, 1996) and memantine (Reisberg, et al, 2003).

c. Neuroanatomical Rules for Brain Structure Boundaries

The hippocampus, parahippocampal gyrus and cingulate gyrus have been selected as the neuroanatomical variables to be assessed during the proposed funding period based on a review of the literature and our own prior results. Explicit neuroanatomical rules were used to define the boundaries of these brain structures. To generate templates, structural boundaries were outlined using semiautomated routines that combine autotracing and manual tracing techniques available in Analyze™. Analyze™ permits the simultaneous viewing of any point in the scan from three orthogonal planes. Autotracing functions encircle a selected region of uniform density by enclosing all contiguous pixels of similar density. The selection of tissue of a particular density is then achieved by setting thresholds that define the brightness of the pixels in the area of interest. Surrounding tissue of a different density (threshold) is deleted from the picture, leaving only the tissue of interest. When autotracing fails to segment tissues of similar density, the tissue is manually traced.

d. MR Scanning Protocols and Image Preprocessing

MR scans will be collected at the baseline assessment and after two years using a 1.5T VISION system (Siemens Medical Systems) with a UNIX based host computer (Sun Microsystems), actively shielded gradients, and echo-planar capability. Subjects will be positioned on the table with their canthomeatal line perpendicular to the table; head position stability is facilitated with adjustable cushioned head supports. A standardization object is placed in the field of view on the left side of the head for each MR scan. Prior to the scan, the

procedure is explained in detail to each subject, and techniques to tolerate small spaces and avoid claustrophobia are described. The MRI scans do not involve the administration of any contrast agent.

All MR scans will be acquired using a turbo-FLASH sequence (TR=20, TE=5.4, Flip angle=30° ACQ-1, Matrix=256X256, Scanning time=13.5 minutes), that 3D datasets with 1 mm x 1 mm x 1 mm isotropic resolution across the entire cranium (Venkatesan and Haacke, 1997). A 2D set of proton density and T2 weighted images with standard 5-mm thicknesses will also be acquired for clinical interpretation of any unsuspected disease conditions, and to assess the number of white matter hyperintensities in each subject. [name], Associate Professor of Radiology, oversees MR scan acquisition at Washington University School of Medicine, and together with his team, monitors scanner drift on a daily basis. Frequency, receiver gain, reference transmitter voltage, and signal-to-noise are examined. Phantoms of known dimensions are imaged and the gradient calibration is checked to make certain the correct size is registered. Protocols are also employed to check for ghosting artifacts. Further tests and calibration adjustments are performed when needed. Shims are used when needed to correct for field inhomogeneities.

For image analysis, the raw MR data are transferred to a SGI workstation at Washington University where 3D reconstructions of brains are obtained using Analyze™ software (Rochester, MN). MR data files are identified by number only to maintain blind conditions for image analysis. Because the turbo-FLASH MR sequence yields 1 mm isotropic voxels, rescaling to correct discrepancies due to voxel isotropy is not necessary. Signed 16 bit MR datasets are compressed to unsigned 8 bit MR datasets by linearly rescaling the voxel intensities, such that voxels with intensity levels at two standard deviations above the white matter mean (corpus callosum) are mapped to 255, and voxels with intensity levels at two standard deviations below the CSF mean (third ventricle) are mapped to 0.

As a final step in the preprocessing of MR images, neuroanatomical landmarks are placed by [name]. In each scan, twelve landmarks are placed at the external boundaries of the brain, and at the points where the anterior and posterior commissures intersect the midsagittal plane (Haller, et al, 1997). Additional landmarks are also placed at selected points along the principal axis of the hippocampus (Csernansky, et al, 1998).

i) *Hippocampus*. The most posterior slice containing the hippocampus is defined when the hippocampus first appears adjacent to the trigone of the lateral ventricle. A narrow band of gray matter along the medial aspect of the trigone opens to a thicker complex of gray matter and is separated from the trigone by a strip of white matter, i.e., the junction of the fimbria and fornix. The coronal slice shows an elongated gray matter shape because of the transverse orientation of the hippocampal tail. This complex is the cornu ammonis (CA), dentate gyrus and subiculum. It is difficult to select a point of separation between the CA and the subiculum because the superior component of the CA does not extend medially far enough to be the landmark of the medial border of the hippocampus, the inferior component of CA is continuous with the subiculum, and there is no gross anatomical separation of the subiculum, presubiculum, and parasubiculum, the lattermost being part of the parahippocampal gyrus. For these reasons, the subiculum and CA are combined in the volume called hippocampus, as has been done by others (Shenton, et al, 1992), and the inferior border of the CA-subiculum is continued medially with a straight horizontal line across the cortex of the parahippocampal gyrus. The cortex below this line is thus considered the parahippocampal gyrus, and the cortex above this line the hippocampus.

Progressing anteriorly from the tail, the orientation of the hippocampus changes from the medial-to-lateral alignment of the tail to the posterior-to-anterior alignment of the body. Thus, the body is cross-sectioned in the coronal slices perpendicular to its long axis, and appears to be divided by the white matter of the fimbria into a lower part that is the CA-subiculum and an upper part formed by the tail of the caudate nucleus. The thalamus appears medial and superior to the CA-subiculum complex.

The thalamus and caudate nucleus form the superior borders of the hippocampus in its posterior aspect. The white matter boundary (alveus and fimbria) between the hippocampus and caudate nucleus as well as any CSF lateral to the hippocampus is not included. The superior and lateral borders of the hippocampal body and head are identified by the contrast against the white matter or CSF. Vessels at the medial aspect of the hippocampus are excluded from the hippocampus. Where the amygdala appears at the superior boundary of the hippocampal head, it as well as the white matter boundary are excluded. However, the vertical digitation of the hippocampal

head which curves up and medial to the amygdala in coronal sections is included. The separation of the amygdala and hippocampus is best achieved by viewing sagittal and transverse sections.

ii) *Parahippocampal Gyrus (including entorhinal cortex)*. Delineation of the structure is made primarily using MR slices oriented in the coronal plane, perpendicular to the AC-PC line. Posteriorly, the parahippocampal gyrus blends imperceptibly with the lingual gyrus of the occipital lobe. It is well known that temporo-occipital separation is not definable. Therefore, the posterior limit of the parahippocampal gyrus is defined as the anterior end of the calcarine sulcus. The same coronal section also defines the posterior limit of the cingulate gyrus, and the parahippocampal gyrus is situated between the notch of the calcarine sulcus below and the cingulate gyrus above.

Moving anteriorly, in coronal sections, the parahippocampal gyrus is limited by the subiculum medially and the collateral sulcus laterally. The anterior limit is defined by the rhinal sulcus which runs from lateral to medial, separating the parahippocampal gyrus from the temporal pole. The rhinal sulcus is identified in the axial section that shows the amygdala, head of hippocampus and uncal recess of the temporal horn. The sweep of the ambient gyrus over the medial aspect of amygdala in the axial section ends at a notch where the temporal pole begins. This notch is the rhinal sulcus. In coronal sections anterior to the amygdala, the superior limit of the parahippocampal gyrus is defined as the inflection point of the white matter at the inferior border of the gray matter of the amygdala.

iii) *Cingulate Gyrus*. The cingulate gyrus is delimited at its ventral aspect by the callosal sulcus, which separates it from the corpus callosum. Dorsally, it is delimited by the cingulate sulcus. Delineation of the structure is made primarily from MR slices oriented in the coronal plane, perpendicular to the AC-PC line.

The cingulate gyrus can be separated into anterior and posterior segments. The posterior limit of the anterior cingulate gyrus is taken to be in the coronal section perpendicular to the midpoint of the AC-PC line. As the cingulate gyrus extends anteriorly and wraps around the genu and rostrum of the corpus callosum, it tapers off gradually. Therefore, the anterior limit of the anterior cingulate gyrus is defined as the most rostral coronal section through the septum pellucidum, and the medial limit of the cingulate gyrus is the cortical surface in the interhemispheric fissure. The superior limit of the cingulate gyrus is the cortical surface forming the inferior bank of the cingulate sulcus (the superior bank being the superior frontal gyrus). This surface extends horizontally in a lateral direction to the fundus of the cingulate gyrus. At this point, a straight horizontal line is drawn through the thickness of the cortex to indicate the separation of the cingulate gyrus and superior frontal gyrus. From the lateral end of this horizontal line in the deep limit of the cortex, a straight line is drawn to the lateral limit of the cortex abutting the superior surface of the corpus callosum and separated from it by the callosal sulcus. The inferior limit of the cingulate gyrus is the inferior surface of the cortex forming the superior bank of the callosal surface (the inferior bank being the corpus callosum).

